14. DATA AND SAFETY MONITORING

14.1 Data Management and Reporting

All patients who received any amount of study drug will be included in the safety analysis. Subjects will be monitored at each clinic visit and at any contact with the subject throughout the study for the occurrence of AEs and SAEs. The investigator or site staff will inquire about the occurrence of AEs/SAEs at weeks 12, 24, 36, and 52. Adverse events will be graded according to the NCI Common Terminology Criteria v. 4.0. All relevant AE's, as described in Section 9.6, that occur during active treatment will be recorded in subject source documents and on CRFs, regardless of relationship to investigational treatment. Non-serious adverse events that occur within the 30 day follow-up period will only be recorded on the CRFs if the investigator believes there to be a possible relationship to study medication. Serious adverse events should be recorded, regardless of relationship to drug.

Safety analyses will include summaries of adverse event rates (both frequency and incidence tables), baseline laboratory parameters and changes from baseline, frequency of CTC toxicity grades for both laboratory and non-laboratory data. The investigators and others responsible for patient care at individual sites should institute any supplementary investigations of major adverse events based on their clinical judgment of the likely causative factors.

14.2 Meetings

We will utilize the Data and Safety Monitoring Plan of the Dan L. Duncan Cancer Center at Baylor College of Medicine. During the clinical trial, clinical data on all participants enrolled on the study will be reviewed in our monthly breast center Data and Safety Monitoring Meeting.

We will have the trial reviewed at our Data Review Committee which will review accruals, serious adverse events, and cumulative toxicity data. The DRC will make recommendations about safety and tolerability.

15. REGULATORY CONSIDERATIONS

15.1 Protocol Review and Amendments

Information regarding study conduct and progress will be reported to the Institutional Review Board (IRB) per the current institutional standards of each participating center. Any changes to the protocol will be made in the form of an amendment and must be approved by the IRB of each institution prior to implementation. The Protocol Chair (or his designee) is responsible for the coordination and development of all protocol amendments, and will disseminate this information to the participating centers.

15.2 Informed Consent

An investigator will explain to each subject the nature of the study, its purpose, the procedures involved, the expected duration, the potential risks and benefits involved and any discomfort it may entail. Each subject will be informed that participation in the study is voluntary, that s/he may withdraw from the study at any time, and that withdrawal of consent will not affect her subsequent medical treatment or relationship with the treating physician(s) or institution. The informed consent will be given by means of a standard written statement, written in non-technical language, which will be IRB approved. The subject should read and consider the statement before signing and dating it, and will be given a copy of the document. No subject will enter the study or have study-specific procedures done before his/her informed consent has been obtained.

In accordance with the Health Information Portability and Accountability Act (HIPAA), the written informed consent document (or a separate document to be given in conjunction with the consent document) will include a subject authorization to release medical information to the study investigator and supporting agencies and/or allow these bodies, a regulatory authority, or

Institutional Review Board access to subjects' medical information that includes all hospital records relevant to the study, including subjects' medical history.

15.3 Ethics and GCP

This study will be carried out in compliance with the protocol and Good Clinical Practice, as described in:

1. ICH Harmonized Tripartite Guidelines for Good Clinical Practice 1996.
2. US 21 Code of Federal Regulations dealing with clinical studies (including parts 50 and 56 concerning informed consent and IRB regulations).
3. Declaration of Helsinki, concerning medical research in humans (Recommendations Guiding Physicians in Biomedical Research Involving Human Subjects, Helsinki 1964, amended Tokyo 1975, Venice 1983, Hong Kong 1989, Somerset West 1996).

The investigator agrees to adhere to the instructions and procedures described in it and thereby to adhere to the principles of Good Clinical Practice that it conforms to.

16. MULTI-CENTER GUIDELINES

16.1 Study Documentation

Each participating site is responsible for submitting copies of all relevant regulatory documentation to the Coordinating Center. The required documents include, but are not limited to the following: local IRB approvals (i.e., protocol, consent form, amendments, patient brochures and recruitment material, etc.), IRB membership rosters, summary of unanticipated problems or protocol deviations, and documentation of expertise of the investigators. The Coordinating Center will provide each participating site with a comprehensive list of the necessary documents. It is the responsibility of the participating sites to maintain copies of all documentation submitted to the Coordinating Center.

The requirements for data management, submissions, and monitoring are outlined below.

All data collected will be entered by the participating site into the Coordinating Center Electronic Database (eCRF), via ONCORE.

16.2 Records Retention

Following closure of the study, each participating center will maintain a copy of all site study records in a safe and secure location. Records must be maintained for at least 5 years following

the conclusion of the study, or in accordance with institutional policy, whichever is longer. The Coordinating Center will inform the investigator at each site at such time that the records may be destroyed.

47. van Groen M, ten Klooster P, Taal E, van de Laar M, Glas C. Application of the health assessment questionnaire disability index to various rheumatic diseases. *Qual Life Res*. Nov 2010;19(9):1255-63.

18. Appendix A: Health Assessment Questionnaire (HAQ)

HEALTH ASSESSMENT QUESTIONNAIRE©Stanford University School of Medicine
Division of Immunology & Rheumatology**Name** _____**Date** _____

In this section we are interested in learning how your illness affects your ability to function in daily life. Please feel free to add any comments on the back of this page.

Please check the response which best describes your usual abilities OVER THE PAST WEEK

Without ANY difficulty ⁰	With SOME difficulty ¹	With MUCH difficulty ²	UNABLE to do ³
-------------------------------------	-----------------------------------	-----------------------------------	---------------------------

DRESSING & GROOMING

Are you able to:

-Dress yourself, including tying shoelaces and doing buttons?				
-Shampoo your hair?				

ARISING

Are you able to:

-Stand up from a straight chair?				
-Get in and out of bed?				

EATING

Are you able to:

-Cut your meat?				
-Lift a full cup or glass to your mouth?				
-Open a new milk carton?				

WALKING

Are you able to:

-Walk outdoors on flat ground?				
-Climb up five steps?				

Please check the response which best describes your usual abilities **OVER THE PAST WEEK:**

	Without ANY difficulty⁰	With SOME difficulty¹	With MUCH difficulty²	UNABLE to do³
HYGIENE				
Are you able to:				
-Wash and dry your body?				
-Take a tub bath?				
-Get on and off the toilet?				
REACH				
Are you able to:				
-Reach and get down a 5-pound object (such as a bag of sugar) from just above your head?				
-Bend down to pick up clothing from the floor?				
GRIP				
Are you able to:				
-Open car doors?				
-Open jars which have been previously opened?				
-Turn faucets on and off?				
ACTIVITIES				
Are you able to:				
-Run errands and shop?				
-Get in and out of a car?				
-Do chores such as vacuuming or yardwork				

We are also interested in learning whether or not you are affected by pain because of your illness.

How much pain have you had because of your illness IN THE PAST WEEK:

PLACE A VERTICAL (|) MARK ON THE LINE TO INDICATE THE SEVERITY OF THE PAIN

NO PAIN	<hr style="width: 100px; border: 0; border-top: 1px solid black; margin-left: 10px; margin-right: 10px;"/>	SEVERE PAIN
0	100	

APPENDIX B STUDY CALENDAR

Study Procedure	Baseline (- 28 d)	Week 4	Wk 12	W 24	W 36	W 52	EOT	Safety Follow-up ² (+/- 7 d)	Follow-up for recurrence ³ (+/- 30 d)
Informed Consent	X								
Demographics	X								
Medical history	X								
Body weight measurement	X		X	X	X	X	X		
Health Assessment Questionnaire	X		X			X	X		
Grip Strength Measurement	X		X			X	X		
Review concomitant meds	X		X	X	X	X	X		
Bone Mineral Density Test ⁴	X								
Adverse Event Assessment			X	X	X	X	X	X	
Assess compliance ¹			X	X	X	X	X		
Assess disease & vital status									X
Calcium, Albumin, and 25(OH) Vit D levels	X	X	X	X	X	X	X		

1. Compliance assessment as determined by pill count and/or pill diary.
2. A safety follow-up should be performed 30 days after the last dose of study medication, even in the event of early discontinuation. Physical exam and laboratory assessments need only be performed if clinically indicated.
3. Recurrence follow ups will be performed every 6 months for the 4 years following the completion of the 52 week study period.

Study Procedure	Baseline (- 28 d)	Week 4	Wk 12	W 24	W 36	W 52	EOT	Safety Follow-up² (+/- 7 d)	Follow-up for recurrence³ (+/- 30 d)
------------------------	-----------------------------	-------------------------	--------------	-----------------------	-----------------------	-----------------------	------------	--	---

4. The Bone Mineral Density test must be ordered as a screening assessment, and results must be available within 28 days of starting AI therapy. If not completed within 28 days, patient will be taken off trial.

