6.5 Follow up at week 52, and End of Treatment Visit

The following assessments should be performed within five to ten business days of the completion of study therapy. End of treatment is defined as Week 52. These assessments should also be performed for patients who discontinue treatment prematurely (unless otherwise noted below).

- Measurement of body weight and BMI
- Laboratory assessments to include calcium level, 25-hydroxyvitamin D, and albumin.
- Patient is to complete the Health Assessment Questionnaire (HAQ-II)
- Grip strength measurement
- Record all concomitant medications added and/or changed.
- Assess compliance to aromatase inhibitor therapy
- Assess compliance to vitamin D and calcium treatment

Non-serious and serious adverse events should be recorded and graded appropriately as discussed in section 9.6.

At this point, patients will have completed study treatment and should proceed with the completion of their adjuvant therapy, as determined by the treating physician. Patients may take Vitamin D at any dosage they wish, at the discretion of the patient and the treating physician.

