6.6 Safety Follow-up

6.7 Upon completion of the therapeutic regimen, subjects will be followed for adverse events for a period of 30 days after the last dose of Vitamin D on study. Patients with abnormal laboratory or clinical findings that are believed to be treatment related will be followed until the condition resolves, stabilizes, or until the laboratory values are no longer considered clinically significant. New adverse events that occur during the 30 day follow-up period will only be recorded if the investigator believes there is a reasonable possibility that the adverse event is drug-related. The safety follow-up may be conducted by a phone visit or a clinic visit; if clinically indicated, a clinic visit should be performed along with relevant lab work. Per standard of care and NCCN guidelines, bone density scan will be repeated, at the treating physician's discretion, every 1-2 years while the patient is on AI therapy. Per NNCN guidelines, patient will have DEXA scan every 2 years while on AI therapy, or every year if accelerated bone loss is suspected, or therapeutic intervention applied. Duration of Follow-up

All subjects will be followed for breast cancer recurrence at approximately 6-month intervals from the completion of the study period (52 weeks) to the completion of the five years of adjuvant therapy. Follow-ups may be conducted by phone, email, or clinic visit, and will be discontinued in the event of subject death, recurrence, loss to follow up after at least 3 documented attempts to contact her, or withdrawal of consent.

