9. ADVERSE EVENTS & SAFETY MONITORING

9.1 General

Adverse event collection and reporting is a routine part of every clinical trial. This study will use the descriptions and grading scales found in the NCI Common Terminology Criteria for Adverse Events version 4.0 (CTCAE v4.0) that is available at <http://ctep.cancer.gov/reporting//ctc.html>.

Information on certain adverse events, whether reported by the participant, directly observed, or detected by physical examination, laboratory test or other means, will be collected, recorded, followed and reported as described in the following sections.

Adverse events experienced by participants will be collected and reported from initiation of study medication, throughout the study, and within 30 days of the last dose of study medication. Participants who experience an ongoing adverse event related to a study procedure and/or study medication beyond 30 days will continue to be contacted by a member of the study team until the event is resolved, stabilized, or determined to be irreversible by the participating investigator.

Participants should be instructed to report any serious post-study event(s) that might reasonably be related to participation in this study. The investigator should notify the IRB and any other applicable regulatory agency of any unanticipated death or adverse event occurring after a participant has discontinued or terminated study participation that may reasonably be related to the study.

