9.5 Adverse event follow-up

Investigators should follow-up subjects with adverse events until the event has subsided (disappeared) or until the condition has stabilized. Subjects will be followed for adverse events and serious adverse events for 30-days from the last dose of study drug.

During the 30-day follow-up period, new onset, non-serious adverse events should only be recorded if, in the opinion of the investigator, there is a reasonable possibility the event is attributable to the investigational product. All serious adverse events occurring within the 30-day follow-up period must be reported, regardless of suspected causality.

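### The ±7-day window in Appendix B lets the last scheduled adverse event inquiry fall on day 23, up to 7 days before the 30-day safety period ends

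*Combined protocol and SAP*

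**What the plan says.** **The required period.** The text under the Section 6.6 heading (numbered 6.7) says that "subjects will be followed for adverse events for a period of 30 days after the last dose of Vitamin D on study". Section 9.1 collects adverse events from the start of study medication, "throughout the study, and within 30 days of the last dose of study medication". Section 9.5 repeats the period, "Subjects will be followed for adverse events and serious adverse events for 30-days from the last dose of study drug", and adds: "All serious adverse events occurring within the 30-day follow-up period must be reported, regardless of suspected causality". Section 9.6.3 places the same duty on the investigator for serious events, related or not. New non-serious events in these 30 days are recorded only if the investigator thinks a drug relationship reasonably possible (Sections 6.6/6.7, 9.5 and 14.1).

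**The contact that serves it.** Appendix B, footnote 2: "A safety follow-up should be performed 30 days after the last dose of study medication, even in the event of early discontinuation". The column heading gives a symmetric window of 7 days. Section 6.6/6.7 settles the form: "The safety follow-up may be conducted by a phone visit or a clinic visit".

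**The contacts on either side.** The end-of-treatment visit also records adverse events. Section 6.5 times it as follows: "The following assessments should be performed within five to ten business days of the completion of study therapy". Afterwards, footnote 3 of Appendix B says: "Recurrence follow ups will be performed every 6 months for the 4 years following the completion of the 52 week study period". In the recurrence column the calendar marks only disease and vital status.

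**The concern.** A follow-up contact can ask only about what has already happened. If it may be made before the safety period closes, the remaining days have no scheduled inquiry. No section requires a second contact when the first is early.

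What is at stake is the completeness of the post-treatment safety data. That means serious events of any cause, and non-serious events possibly related to the drug, in the last week of the 30 days. Footnote 2 also covers women who stop early. Under Section 6.12 these include women stopped for high 25-hydroxyvitamin D, high calcium or symptomatic renal stones, in whom late events are of most interest. With up to 5 centers scheduling their own calls, the length of time actually observed could also differ between sites.

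**Working it through.** Take the last dose as day 0, and assume that completion of study therapy in Section 6.5 means the same day.

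**Inputs**

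| Item | Value | Source |
|---|---|---|
| Required adverse event period | through day 30 | Sections 6.6/6.7, 9.1, 9.5, 9.6.3 |
| Nominal day of safety follow-up | day 30 | Appendix B, footnote 2 |
| Window | ±7 days | Appendix B, column heading |
| End-of-treatment visit | 5 to 10 business days, about 7 to 14 calendar days | Section 6.5 |
| Next contacts | every 6 months, no adverse event assessment marked | Appendix B and footnote 3 |

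**Allowed contact days.** Earliest: 30 − 7 = day 23. Latest: 30 + 7 = day 37. The number of allowed days is 37 − 23 + 1 = 15.

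**Days left uncovered by a contact on day d.** This is max(0, 30 − d).

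- d = 23: 30 − 23 = 7 days (days 24 to 30), and 7/30 = 23% of the period.
- d = 27: 30 − 27 = 3 days, and 3/30 = 10%.
- d = 30 or later: 0 days.

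**Does an earlier contact cover the gap?** No. The end-of-treatment visit falls at about days 7 to 14, before day 23.

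**Does a later contact cover it?** Not by schedule. The safety follow-up is the last column marked in the adverse event row, and the recurrence contacts begin months later.

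**How many women?** The documents give no distribution of contact days. The share contacted before day 30 can lie anywhere from 0% to 100%, and the mean uncovered time anywhere from 0 to 7 days.

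**With a window of 0 / +7.** Allowed days are 30 to 37, which is 37 − 30 + 1 = 8 days. The largest uncovered time is max(0, 30 − 30) = 0 days.

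**The case against.** The strongest reply is that a visit window says when a call may be made and does not end the reporting period. Sections 9.1, 9.5 and 9.6.3 set the 30-day duty independently of any visit, so a site that calls on day 23 must still report a serious event on day 28 if it learns of one. That stands. A reader might infer that the calendar contradicts the reporting rule or releases the site from it. The documents do not support this, because both texts can be followed at once. The weakness is in how events come to be known: the one-business-day clock in Section 9.6.3 starts only when someone becomes aware.

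Three mitigations also deserve weight.

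- Section 9.1 has women told to report serious events that might reasonably be related to taking part. This leaves out unrelated serious events, which Section 9.5 requires, and related non-serious ones.
- Section 14.1 has subjects monitored for adverse events whenever there is contact with them during the study. This can be read to include recurrence contacts, and vital status there would bring deaths to light. But the calendar marks no adverse event assessment at those contacts, and Section 14.1 names specific inquiry only at weeks 12, 24, 36 and 52.
- Little is at stake in numbers of events. Non-serious events count only if possibly drug-related, and Section 9.6.2 narrows reporting further. After week 52, Section 6.5 lets women take vitamin D at any dosage, so for completers these days are not a clean off-treatment period.

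These points reduce the gap. None of them puts a scheduled inquiry at or after day 30.

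**Conclusion.** The point holds as a minor weakness in safety ascertainment. A fully compliant contact can leave up to 7 of the 30 required days (23%) after the last scheduled adverse event inquiry. The day count needs only the stated period and window, with the last dose as day 0.

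Three stronger readings are tempting and should not be drawn:

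- **That this is the only post-treatment safety contact.** The end-of-treatment visit is another. It simply comes too early to cover days 24 to 30.
- **That events in that week are certain to be lost.** The mitigations in Sections 9.1 and 14.1 mean that they may be learned late or missed, and no event rate is given.
- **That a known fraction of women is affected.** Spreading contacts evenly over days 23 to 37 would give 7/15 = 47% contacted before day 30 and a mean gap of (7+6+5+4+3+2+1)/15 = 28/15 = 1.9 days. Nothing in the documents supports an even spread. If sites aim at day 30, as footnote 2 directs, both figures could be smaller.

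The primary endpoint, alpha and power are not touched.

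**What to change.** Make the window in the Appendix B heading one-sided: *Safety Follow-up (0 / +7 d)*. Add to footnote 2 that the contact takes place on or after day 30 and asks about all adverse events through day 30. Sections 6.6/6.7, 9.1, 9.5 and 9.6.3 need no change.

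The cost is a scheduling window of 8 days in place of 15. No visit is added: the same single contact, by phone or in clinic, can no longer be made early. The largest uncovered time falls from 7 days to 0.

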4. PARTICIPANT SELECTION

4.1 Inclusion Criteria

- 4.1.1 All participants must be female and at least 21 years of age
- 4.1.2 Signed informed consent
- 4.1.3 Patients must have had histologically confirmed stage I-III breast carcinoma that is positive for Estrogen Receptor (ER) and/or Progesterone Receptor (PR).
- 4.1.4 Post-menopausal status defined by any of the following:
 - Age >60 years
 - History of bilateral oophorectomy
 - Serum estradiol and FSH concentrations in the post-menopausal range, along with either amenorrhea for 12 months or previous hysterectomy (If patient is <60 years old, post-menopausal status must have been confirmed PRIOR to chemotherapy, if chemotherapy was given)
- 4.1.5 Beginning adjuvant aromatase inhibitor therapy, with no previous use within the last 6 weeks. Patients may take anastrozole, letrozole, or exemestane, per the discretion of the treating physician and the patient.
- 4.1.6 Bisphosphonates are allowed, at the treating investigator's discretion
- 4.1.7 Performance status (WHO/ECOG scale) 0-2.

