6.1 Screening and Baseline assessments

A signed, written informed consent must be obtained before any study-specific assessments are initiated. Results from assessments performed prior to written consent as part of a patient's routine diagnostic workup may be used for screening purposes. The following assessments will be obtained at screening, within 28 days prior to beginning study medication:

- Subject demographic information, to include age, ethnicity, and race
- Medical history, including past and current conditions, and past surgical history
- Whether patient has used Hormone Replacement Therapy (HRT), for how many years, and how long ago she stopped.
- Use of chemotherapy, including taxanes or not including taxanes
- Measurement of body weight, height, and Body Mass Index
- Completion of Health Assessment Questionnaire (HAQ-II)

- Grip strength measurement
- Laboratory assessments to include:
 - Calcium level
 - Albumin level
 - Vitamin D level -- serum 25(OH)D
 - FSH, LH, and estradiol levels must be obtained if required as detailed above in 4.1.4 to determine menopausal status. Menopausal status should be interpreted by the treating physician and approved by study chair based on the cutoff values provided by the reporting laboratory.
- Review of all medications taken within 28 days of planned treatment start date
- Study coordinator will educate the patient about the importance of compliance with Aromatase Inhibitor therapy.
- If a Bone Mineral density test has not been completed within 3 months of starting AI therapy, a Bone Mineral Density test must be ordered as a screening assessment, and the test must be completed within 28 days of starting Aromatase Inhibitor therapy

If the above studies are within acceptable parameters as defined by the eligibility criteria, the patient will be randomized to begin either high dose Vitamin D or standard dose Vitamin D, as described in [Section 7](#).

6.2 Follow-up at Week 4

The following assessments should be performed at 4 weeks (28 days) from the start of study medication. To allow for weekends, holidays, etc., study procedures may be completed within a window of +/- 5 business days.

- Laboratory assessments to include a calcium level, 25-hydroxyvitamin D level, and albumin.

6.3 Follow-up at Week 12

- Measurement of body weight and BMI
- Laboratory assessments to include a calcium level, 25-hydroxyvitamin D level, and albumin.
- Patient is to complete the Health Assessment Questionnaire (HAQ-II)

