6.14 Criteria for Removal from the Study

Participants will be removed from study when any of the criteria listed in Section 6.12 applies. All patients who are randomized in the study will be included in the overall evaluation of response (intent-to-treat analysis). All reasons for discontinuation of therapy should be documented clearly in the medical record.

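### Section 6.1 and Appendix B footnote 4 state the bone-density requirement differently, and its deadline can be read as falling after randomisation, so a late scan could cost a randomised woman's week-12 outcome

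*Combined protocol and SAP*

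**What the plan says.** Section 6.1 puts the scan in a list introduced by "The following assessments will be obtained at screening, within 28 days prior to beginning study medication". The scan item has its own condition: "If a Bone Mineral density test has not been completed within 3 months of starting AI therapy", one must be ordered as a screening assessment and "the test must be completed within 28 days of starting Aromatase Inhibitor therapy". No consequence of lateness is given. The section then says "If the above studies are within acceptable parameters as defined by the eligibility criteria, the patient will be randomized" to one of the two arms.

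Appendix B marks the scan in the baseline column only. Footnote 4 repeats that it is ordered at screening, states that "results must be available within 28 days of starting AI therapy", and ends "If not completed within 28 days, patient will be taken off trial". It does not mention the 3-month exemption.

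Four other provisions bear on this:

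- Section 6.14: "Participants will be removed from study when any of the criteria listed in Section 6.12 applies". The Section 6.12 list has no item for a bone-density scan.
- Section 5.2 allows the protocol chair to accept women whose baseline studies are slightly out of window, without this counting as a protocol exception.
- Section 12.1.2 keeps all randomised women in the analysis. It counts a woman who began study medication but has no week-12 HAQ as having developed AI-induced arthralgia (AIA).
- Section 4.1.5 describes the population as "Beginning adjuvant aromatase inhibitor therapy, with no previous use within the last 6 weeks". It does not fix the order of AI start, randomisation and first dose of vitamin D.

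**The concern.** A screening requirement should be settled before randomisation and should read the same wherever it appears. Here the exemption is in one place, the penalty in another, and the event that meets the deadline differs between them. If the deadline falls after randomisation, a woman could leave the trial for a scheduling reason that has nothing to do with treatment or joint symptoms. She would stay in the intent-to-treat set, but her week-12 outcome could be assigned as AIA instead of observed. Up to 5 centers may apply the two texts differently.

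**Working it through.** **1. The two texts side by side**

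| Element | Section 6.1 | Appendix B footnote 4 |
|---|---|---|
| Exemption for a scan within 3 months of AI start | Yes | Not repeated |
| Event that meets the deadline | Test completed | Results available; the removal sentence then reverts to completion |
| Time limit | 28 days of starting AI | 28 days of starting AI |
| Consequence of missing it | None stated | Taken off trial |

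Footnote 4 does not say whether being off trial means stopping study medication, stopping follow-up, or both. Its ground for removal is absent from 6.12, the list on which 6.14 relies.

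**2. Can the deadline fall after randomisation?** Other screening items are timed before study medication. The scan limit is tied to AI start with no direction (before or after), and the scan need only be ordered at screening. Randomisation depends on results meeting the eligibility criteria, but neither 4.1 nor 4.2 mentions bone density, so that check cannot catch a missing scan. Removal from the trial also presupposes a woman already on it. A deadline after randomisation is therefore a permitted reading, though not the only one.

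**3. Route to the primary endpoint.** Section 3 sets the endpoint after 12 weeks of AI therapy, which is 84 days. Read as running after AI start, the 28-day limit comes 84 − 28 = 56 days earlier. The premature-discontinuation visit (6.5, 6.12) does collect a HAQ-II, but at discontinuation. Around day 28 that is also earlier than the median symptom onset of 1.6 months given in Section 1.2. Under 12.1.2 a woman who had begun study medication and has no week-12 HAQ is counted as AIA. For a randomised woman removed before her first dose, 12.1.2 gives no such rule.

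**4. Size.** Inputs from 13.2 are AIA rates of 33% (standard dose) and 19% (high dose), one-sided alpha 0.10, 80% power, 5% dropout and 93 per arm.

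Reproducing the base size in 13.7, with pooled variance and no continuity correction:

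n = [1.2816·√(2·0.26·0.74) + 0.8416·√(0.33·0.67 + 0.19·0.81)]² / 0.14² = 87.6, so 88 per group, as stated. Allowing for 5% dropout, 88/0.95 = 92.6, so 93.

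If a share x of each arm is counted as AIA, the rates become 0.33 + 0.67x and 0.19 + 0.81x, and the difference becomes 0.14(1 − x). Power at n = 93 is

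Φ{[(p1 − p2)√93 − 1.2816·√(2·p̄(1 − p̄))] / √(p1(1 − p1) + p2(1 − p2))}.

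The right comparator already contains the planned 5%. The documents give no removal rate, so 1% to 10% is an assumed range.

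| Extra removals | Women of 186 | Total x | AIA rates (%) | Power | Change |
|---|---|---|---|---|---|
| 0 | 0 | 5% | 36.35 vs 23.05 | 76.1% | – |
| 1% | 1.9 | 6% | 37.02 vs 23.86 | 75.0% | −1.1 points |
| 2% | 3.7 | 7% | 37.69 vs 24.67 | 73.9% | −2.2 points |
| 5% | 9.3 | 10% | 39.70 vs 27.10 | 70.7% | −5.4 points |
| 10% | 18.6 | 15% | 43.05 vs 31.15 | 65.6% | −10.5 points |

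These are fixed-sample figures that ignore the futility look. They assume equal shares in both arms, and that every such woman had begun study medication and has no week-12 HAQ.

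**The case against.** The best defence is that the scan is a baseline item throughout. It sits in the 6.1 screening list and in the baseline column, and randomisation comes after that list. Section 6 calls the calendar a summary, so footnote 4 may be shorthand for the second half of the 6.1 sentence, with the exemption still in force. Section 5.2 softens the penalty for a slightly late scan, and Section 13.3 has both the site PI and the coordinating center confirm eligibility before randomisation. This defence makes deadlines after randomisation less likely, and it rules out saying that sites will diverge; they may. It does not remove the differences in wording, supply a scan item for the eligibility check, or explain a removal ground missing from 6.12.

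Three stronger readings are tempting, and the documents do not support them:

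- A reader might infer that a woman scanned two months before AI start satisfies 6.1 but must be removed under footnote 4. That follows only if the footnote sets a maximum scan age or requires a new scan of everyone. Read as a deadline, her scan is completed.
- A reader might infer that removed women leave the analysis. Sections 6.14 and 12.1.2 keep every randomised woman in it.
- A reader might attribute to this rule a fall in power from 81.8% (93 per arm, nothing missing) to 76.1%. That fall is what 12.1.2 does to the planned 5% dropout with no scan removals at all. Only the increments below 76.1% could belong to the scan rule, and they are the general effect of 12.1.2 at assumed rates.

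**Conclusion.** The inconsistency is real on exemption, deadline event and consequence, and the removal ground conflicts with 6.12/6.14 and fits poorly with 5.2. A deadline after randomisation is a permitted reading. If it is followed, a late scan can turn an observable week-12 outcome into an assumed AIA, for a scan that no eligibility criterion or endpoint uses.

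The effect is probably small. It depends on a removal rate that the documents do not give, on the removed women having begun study medication, and on their having no week-12 HAQ. At an assumed 1% to 2% extra, power falls by 1 to 2 points beyond what planned dropout already costs; it matters more only if missed scans are common. The point is worth correcting because the correction is cheap and protects the primary endpoint. It does not undermine the design.

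**What to change.** 1. Reconcile Section 6.1, Appendix B footnote 4, Sections 6.12/6.14 and Section 5.2 into one rule covering the exemption, the event that meets the deadline, and the consequence of missing it. Say what being off trial means.
2. Add a line to the eligibility worksheet (Section 5.1) confirming before randomisation that the reconciled requirement is met. A booked appointment alone would leave the deadline after randomisation.
3. State that a randomised woman whose scan is late stays in follow-up for the week-12 HAQ-II and pain score, with the late scan recorded as a deviation.

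Which scan interval applies, and whether study medication continues, are for the sponsor to reconcile; no view is offered here.

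The cost is a few lines of text and one worksheet item. The downside is that a few late scans become recorded deviations.
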